Study protocol

Immune monitoring to facilitate belatacept monotherapy

1. Synopsis

Title	Immune monitoring to facilitate belatacept monotherapy
Study design	Prospective single-center, single-arm pilot study
Study center	Massachusetts General Hospital
Principal investigator	[name]
Co-investigators	[name]
Objectives	
1. To determine the percent of belatacept-treated renal transplant patients that can be safely converted to belatacept monotherapy2. To determine the utility of novel immune monitoring tools to facilitate belatacept monotherapy
Primary endpoint	Occurrence of biopsy-proven acute rejection
Secondary endpoints	
- Change in eGFR (CKD-EPI)- Appearance of proteinuria- Appearance of de novo donor-specific antibodies- Overall and death-censored graft survival
Sample size	20
Summary of inclusion criteria	
- Age 18 years or older- Written informed consent- Single kidney transplant recipient (i.e. no combined organ transplants)- Treated with belatacept- At least 1 year after transplantation or after initiation of belatacept- Stable renal function- Blood biomarkers indicate immune quiescence- No history of biopsy-proven acute rejection- Absence of donor-specific antibodies (at any MFI)- No history of BK viremia in current allograft

	
 - Spot urine protein/creatinine ratio < 0.5 g/g
Maximum duration of follow-up per participant	24 months after inclusion
Protocol version	Version 1.4 (10/25/2019)
Version and date of protocol amendments	N/A

2. Background

Belatacept is a selective costimulation blocker that is a non-nephrotoxic alternative to the calcineurin inhibitors cyclosporine and tacrolimus. In renal transplantation, belatacept has demonstrated similar graft and patient survival compared with cyclosporine, but is associated with superior renal function and lower rates of donor specific antibody (DSA) development.^{1,2}

Like calcineurin inhibitors, belatacept is generally prescribed as part of an immunosuppressive regimen that includes either mycophenolic acid (MMF) or and mTOR inhibitor (mTORi) and steroids. Clinical experience suggests that in a significant proportion of belatacept-treated patients, MMF, mTORi and/or steroids can be reduced or even stopped, likely because they have reached a state of partial immunological tolerance. However, true personalization of immunosuppressive therapy, i.e. delivering the minimum amount of immunosuppression necessary to prevent kidney graft rejection for any given patient, is not yet possible because of a lack of reliable tests to monitor the degree of alloimmune reactivity in a kidney graft. So-called protocol biopsies are useful in this respect, but are invasive and suffer from sampling bias and inter-observer variability.

Several non-invasive immune monitoring tools have recently been developed that may aid in the personalization of immunosuppressive therapy. Two in particular are the focus of the current study. First, the presence of donor-derived cell-free DNA (dd-cfDNA) in the blood of kidney transplant recipients has been demonstrated to reflect graft injury.³⁻⁶ Very high values are a strong predictor of antibody-mediated rejection and low values (<1%) exclude active rejection with a negative predictive value of up to 98%.⁷ Second, a blood-based gene expression array (Trugraf™) can predict subclinical rejection in stable allografts with a negative predictive value of 78-88%.⁸

Whether patients with both dd-cfDNA levels < 1% and a Trugraf profile compatible with a state of immunological quiescence can safely undergo a reduction in the intensity of their immunosuppressive regimen has not been explored. In the current study, this hypothesis will be tested in belatacept-treated patients because they have a relatively high a priori likelihood of being in a state of immunological quiescence, which is also reflected by low rejection rates (<1%) after the first posttransplant year.⁹

3. Trial objectives and Design

3.1 Trial objectives

- To determine the utility of novel blood-based immune monitoring tools (Allosure and Trugraf) to facilitate belatacept monotherapy.

- To determine the percent of belatacept-treated renal transplant patients that can be safely converted to belatacept monotherapy.

3.2 Trial design

Prospective single-center, single-arm interventional pilot study

3.3 Primary endpoint at 24 months

- Occurrence of biopsy-proven acute rejection

3.4 Secondary endpoints at 24 months

- Change in eGFR (CKD-EPI)
- Appearance of proteinuria
- Appearance of de novo donor-specific antibodies
- Overall and death-censored graft survival

4. Selection and withdrawal of subjects

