4.2 Exclusion criteria

- History of biopsy-proven acute rejection
- Presence of donor-specific antibodies (at any MFI)
- Spot urine protein/creatinine ratio > 0.5 g/g

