4.4 Withdrawal of subjects

Subjects will be withdrawn from the trial in case of:

- Refusal of the subject to continue
- For any other reason deemed necessary by the investigator and in the interest of the subject.

In the following circumstances, subjects will continue to be monitored in the study but immunosuppression will not be weaned further:

- Either one of the immune monitoring tests are positive at any point (Allosure > 1% or Trugraf signature compatible with rejection)
- Occurrence of biopsy-proven acute rejection (Banff 2017 criteria)
- Occurrence of new proteinuria > 0.5 g/g creatinine, confirmed on repeat urine sample after 2-4 weeks
- Occurrence of de novo donor-specific antibodies at any MFI
- Decrease in eGFR > 20% from baseline without alternative explanation, confirmed on repeat urine sample after 2-4 weeks

5. Trial Procedures

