5.1 By visit

For all belatacept-treated patients, monthly visits in the outpatient clinic, where belatacept infusions are administered, are part of routine clinical care. Trial visits will coincide with these infusion visits, occurring monthly for the first year after inclusion. At study visits, subjects are questioned and examined by a physician and blood samples are drawn (see below). For patients who receive monthly belatacept infusions at home, they will have blood samples (clinical and research specimens) drawn at their local Quest laboratory and the study physician will call them to assess for adverse events. If any adverse events are noted, a telemedicine or in-person visit with a transplant nephrologist will be scheduled at the discretion of the investigator.

Reduction of immunosuppression occurs in a stepwise fashion, whereby each reduction is contingent on several factors:

- Renal function is stable, defined as eGFR no more than 20% lower compared to value at inclusion
- Both the Allosure and Trugraf tests indicate a state of immune quiescence. For the Allosure, this corresponds to a dd-cfDNA concentration of < 1%; for the Trugraf test, this corresponds to a "TX" signature.
- No appearance of any de novo DSA (at any MFI) at any previous point during study
- No proteinuria > 0.5 g/g creatinine on spot urine sample

If, at any point, a patient does not fulfill all of the abovementioned criteria, immunosuppression will not be (further) reduced. In such cases, the principal investigator will decide whether to continue with the reduced-intensity immunosuppressive regimen or revert back to conventional triple therapy (belatacept + mycophenolate/mTORi + steroids).

Criteria for performing a kidney biopsy are:

- Unexplained decrease in eGFR > 40% from baseline value
- Occurrence of new proteinuria > 1.0 g/g creatinine on 2 separate random urine samples

The principal investigator can decide to perform a kidney biopsy in patients who do not strictly meet the abovementioned criteria, if the probability of rejection is felt to be high, i.e. a combination of abnormalities such as new DSA and proteinuria < 1 g/g, or a very high (>3%) Allosure result combined with a mild (20%) decrease in eGFR.

In case of a discrepancy between Allosure and Trugraf results (i.e. Allosure < 1% but Trugraf positive for rejection), immunosuppression will not be weaned further.

Study timeline

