Time point	Blood sample including immune monitoring	Urine protein	DSA monitoring	Action if stable renal function, immune quiescence, no de novo DSA, no proteinuria > 0.5 g/g
Inclusion	Yes	Yes	Yes	
Month 1	Yes	Yes		50 % reduction of MMF/mTORi dose
Month 2	Yes			
Month 3	Yes		Yes	
Month 4	Yes	Yes		Stop MMF/mTORi
Month 5	Yes			
Month 6	Yes		Yes	
Month 7	Yes	Yes		Reduction in prednisone to alternating 5mg – 2.5mg
Month 8	Yes			Reduction in prednisone to 2.5mg
Month 9	Yes		Yes	Reduction in prednisone to 2.5mg – 0mg alternating
Month 10	Yes			Stop steroids
Month 11	Yes			
Month 12	Yes	Yes	Yes	

From months 13 through 24, subjects will resume routine (standard of care) clinical monitoring, namely monthly laboratory analyses when they get their belatacept infusion. In addition to this, proteinuria and DSA will be checked at 24 months (which is not standard of care).

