5.2 Laboratory testing and sample shipping

The following laboratory tests are performed at each study visit during the first 12 months:

- Routine laboratory analyses, including complete blood count, basic metabolic panel, total protein, fasting glucose. These analyses will be performed by the Central Laboratory of Massachusetts General Hospital or at the patient's local Quest laboratory.
- Two 10 ml Streck Cell-Free DNA BCT® whole blood tubes are drawn and stored at 7°C pending shipment. Streck tubes are shipped at ambient temperature (between 6° and 37°C) to CareDx using the shipping material and instructions provided by CareDx.
- Two 2.5ml Paxgene® whole blood tubes are drawn and stored at -20°C pending shipment. These tubes are shipped on ice (-20°C) to Transplant Genomics.
- One 10 ml EDTA and one 10 ml SST tube will be collected, centrifuged at 4°C for 10 minutes at 3000 RPM. The resulting 5 ml of EDTA plasma and 5 ml of SST plasma will be stored at -80°C pending possible future analysis (i.e. biobanked).

Donor-specific antibody screening occurs at 1, 4, 7, 10, 12 and 24 months. These analyses will be performed by the HLA laboratory of Massachusetts General Hospital.

6. Statistics

Normality will be tested using the Shapiro-Wilk test. Average eGFR and proteinuria at baseline and 24 months will be compared using paired samples t test. A 2-sided p-value < 0.05 will be considered statistically significant. All analyses will be performed using IBM SPSS Statistics version 23 (IBM, New York, NY). Figures will be generated using Graphpad Prism version 6 (Graphpad Prism, La Jolla, CA).

7. Direct access to source data and document

The investigator and the institution will permit trial-related monitoring, audits, EC review, and regulatory inspections (where appropriate) by providing direct access to source data and other documents (e.g. subjects' case sheets, blood test reports, X-ray reports, histology reports etc).

8. Ethics and regulatory approvals

The trial will be conducted in compliance with the principles of the Declaration of Helsinki (2013), the principles of GCP and in accordance with all applicable regulatory requirements. This protocol and related documents will be submitted for review to the Ethics Committee.

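### New proteinuria is named as a per-patient event, but the only planned analysis compares mean values and does not estimate how many participants developed it

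*Combined protocol and SAP*

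**What the plan says.** The Synopsis and Section 3.4 list "Appearance of proteinuria" among the secondary endpoints. The same lists word the kidney-function endpoint as a change in eGFR, so the protocol itself separates a change in level from an event. The heading of Section 3.4 is "Secondary endpoints at 24 months".

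Section 6 has one sentence on proteinuria: "Average eGFR and proteinuria at baseline and 24 months will be compared using paired samples t test". It gives no count, proportion or interval for new proteinuria, and neither does any other section. Section 6 also says that normality will be checked with the Shapiro-Wilk test, and it names no alternative if the check fails.

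Proteinuria levels appear in several operational rules:

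- Entry: "Spot urine protein/creatinine ratio < 0.5 g/g" (Synopsis) and, as an exclusion, "Spot urine protein/creatinine ratio > 0.5 g/g" (Section 4.2).
- Stopping further weaning: "Occurrence of new proteinuria > 0.5 g/g creatinine, confirmed on repeat urine sample after 2-4 weeks" (Section 4.4).
- Condition for each reduction: "No proteinuria > 0.5 g/g creatinine on spot urine sample" (Section 5.1), repeated in the timeline header as "no de novo DSA, no proteinuria > 0.5 g/g".
- Biopsy: new proteinuria above 1.0 g/g on two separate random samples (Section 5.1).

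Urine protein is scheduled at inclusion, months 1, 4, 7 and 12 (study timeline), and month 24 (text below the timeline).

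**The concern.** A test of mean change suits the eGFR endpoint. Applied to proteinuria, it answers a different question from the one the endpoint asks. A mean can move because a few participants rise a lot or because many rise a little, and only the first pattern need contain anyone with new proteinuria. Followed as written, Section 6 yields a p-value for a mean difference and no estimate of the named endpoint.

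The event also cannot be counted from the text as it stands. Two levels are used for new proteinuria, 0.5 and 1.0 g/g. The 0.5 g/g rules differ on whether a repeat sample is needed, and the window can be read as at month 24 or by month 24. If these choices are left open, they will be made after the data are seen, when a small change of definition could move one or two participants out of 20.

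**Working it through.** **No stated figure to reproduce.** The documents give a sample size of 20 (Synopsis) without an expected proteinuria rate, standard deviation, effect size or dropout rate. The check is therefore a comparison of endpoint and analysis, with an illustration on constructed data.

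**Step 1. Endpoint against analysis.**

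| Item | Endpoint (Synopsis, 3.4) | Analysis (Section 6) |
|---|---|---|
| Unit | Event in a participant | Mean over participants |
| Natural summary | Number with event / number assessable | Mean difference, p-value |
| Samples used | Month 24 alone, or 1, 4, 7, 12 and 24, depending on the window | Baseline and 24 only |
| Threshold | None tied to the endpoint | None needed |

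**Step 2. Does the test result determine the count?** Take n = 20 and count an event as a follow-up value above 0.5 g/g in someone who entered at or below it. The paired t statistic is t = mean change / (SD of change / √20), with 19 degrees of freedom.

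*Dataset A.* Four participants rise by 1.0 g/g and 16 do not change.
- Mean = 4 × 1.0 / 20 = 0.20.
- SD = √[(4 × 0.80² + 16 × 0.20²) / 19] = √(3.20 / 19) = 0.4104.
- t = 0.20 / (0.4104 / √20) = 0.20 / 0.09177 = 2.179, p = 0.042.
- Events: 4/20. A rise of 1.0 g/g crosses 0.5 g/g from any starting value.

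*Dataset B.* All start at 0.20 g/g; 10 end at 0.35 and 10 at 0.15.
- Mean = (10 × 0.15 − 10 × 0.05) / 20 = 0.05.
- SD = √(20 × 0.10² / 19) = 0.1026.
- t = 0.05 / (0.1026 / √20) = 0.05 / 0.02294 = 2.179, p = 0.042.
- Events: 0/20. The highest final value is 0.35 g/g.

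The test results are identical and the counts are 4 and 0. The mean changes differ (0.20 and 0.05 g/g), but neither can be converted into a count without the individual values.

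**Step 3. What a direct estimate gives.** These are exact (Clopper-Pearson) two-sided 95% intervals. For 0/n the upper limit is 1 − 0.025^(1/n), which for n = 20 is 16.8%. The counts are assumed.

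| Events / assessable | Percent | Exact 95% CI |
|---|---|---|
| 0/20 | 0% | 0 to 16.8% |
| 1/20 | 5% | 0.1 to 24.9% |
| 3/20 | 15% | 3.2 to 37.9% |
| 4/20 | 20% | 5.7 to 43.7% |
| 0/18 | 0% | 0 to 18.5% |
| 3/18 | 16.7% | 3.6 to 41.4% |

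The last two rows show the effect of two participants without an assessable sample.

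**Step 4. Limit of the illustration.** The changes in A and B each take only two values and fail a Shapiro-Wilk test (p < 0.00001 in both). Because the plan names no fallback, the t test might still be run on such data. The p-values illustrate the point and do not predict the trial's result.

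**The case against.** The strongest reply is that this is a 20-patient pilot and the endpoint is secondary. The plan does not forbid a count, and the urine results will be available to make one. All of this is true and limits the weight. It does not remove the gap, because the definition of the event would still be chosen after the results are known.

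A second reply is that the illustrations would be flagged by the plan's own normality check. That stands as a limit on the p-values. The conclusion does not depend on them: a mean does not estimate a proportion, whatever the distribution.

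A third is that Section 6 gives no analysis for the other event endpoints either, including the primary one. That is correct and is a wider matter. Proteinuria differs in that an analysis is stated and does not match the endpoint.

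Three stronger readings are tempting, and the documents do not support them:

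- *That 0.5 g/g is the protocol's definition of the endpoint.* It recurs in the entry and weaning rules, but the biopsy rule uses 1.0 g/g for new proteinuria in almost the same terms, and neither is linked to the endpoint.
- *That the Section 3.4 heading fixes the window as status at month 24.* Section 3.3 uses the same form of heading for occurrence of biopsy-proven acute rejection, which is naturally cumulative.
- *That the t test by itself defeats the objective on the percent safely converted.* The protocol does not define safe conversion by this endpoint. Proteinuria gates the weaning steps, so a link is plausible, but it is not stated.

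**Conclusion.** The mismatch holds. The endpoint is a per-patient event, and the only stated analysis is a comparison of means that does not estimate its frequency and uses two of the six scheduled urine samples. Threshold, confirmation and window are all open.

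The illustration shows that one test result (t = 2.179, p = 0.042) is compatible with 4/20 and with 0/20 events. It assumes n = 20 with complete pairs, constructed changes, and an event defined as exceeding 0.5 g/g. A reader should not infer from it a minimum number of affected participants needed for significance, because that number depends on how everyone else's values move.

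The consequence is modest. One secondary endpoint of a pilot would go without an estimate, and no sample-size figure depends on it. The change is still worth making because it is cheap and has to be settled before the data are examined.

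**What to change.** These changes are for the analysis only. All weaning and biopsy rules stay as they are. In Section 6:

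1. Define the endpoint event before the data are seen. A value above 0.5 g/g is suggested as the analysis threshold because it matches the entry limit in Section 4.2, so any later value above it is new relative to entry. A count above 1.0 g/g may be shown as well.
2. State whether a confirming sample is needed and how an unconfirmed month 24 value counts. A repeat 2 to 4 weeks later would fall after the 24-month maximum follow-up in the Synopsis.
3. Report the number with the event, the number assessable, the percent and an exact 95% CI, in two rows: at any scheduled sample after inclusion through month 24, and at month 24. State the window explicitly and do not rely on the Section 3.4 heading.
4. Keep the baseline-to-24-month comparison as a supplementary analysis of level.

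The cost is a few lines of text and one small table, using urine samples already scheduled at months 1, 4, 7, 12 and 24, with no change in sample size. The intervals will be wide, as the table above shows. The gain is an estimate of the named endpoint, not more power. No urine sample is specified between months 12 and 24, so neither row would capture proteinuria that came and went in that year.

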4.1 Inclusion criteria

- Age minimum 18 years
- Written informed consent
- Single kidney transplant recipient (i.e. no combined organ transplants)
- Treated with belatacept
- At least 1 year after transplantation or after initiation of belatacept
- Stable renal function (eGFR > 40 ml/min continuously during previous 6 months)
- Blood biomarkers indicate immune quiescence (for Allosure this corresponds to dd-cfDNA < 1%; for Trugraf this corresponds to "TX" signature)
- No history of BK viremia in current allograft

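### Entry stability is only an eGFR floor of 40, so a decline already under way can pass into the uncontrolled 24-month eGFR comparison unrecognised

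*Combined protocol and SAP*

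**What the plan says.** The protocol gives renal stability two meanings.

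- **At entry (section 4.1):** "Stable renal function (eGFR > 40 ml/min continuously during previous 6 months". The synopsis lists stable renal function without defining it. Nothing in sections 4.1 or 4.2 limits the change in eGFR before inclusion.
- **On study, before each reduction step (section 5.1):** "Renal function is stable, defined as eGFR no more than 20% lower compared to value at inclusion". If a condition fails, "If, at any point, a patient does not fulfill all of the abovementioned criteria, immunosuppression will not be (further) reduced".

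Section 4.4 has its own 20% rule for halting weaning: "Decrease in eGFR > 20% from baseline without alternative explanation", with confirmation on a repeat sample. Section 5.1 has neither the exemption for an explained fall nor the confirmation. The eGFR criterion for biopsy in section 5.1 is "Unexplained decrease in eGFR > 40% from baseline value".

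Change in eGFR is a secondary endpoint at 24 months (section 3.4). Section 6 gives the analysis: "Average eGFR and proteinuria at baseline and 24 months will be compared using paired samples t test". No value from before inclusion enters it. The design is a single arm (section 3.2) of 20 patients (synopsis). One of the two objectives in section 3.1 is: "To determine the percent of belatacept-treated renal transplant patients that can be safely converted to belatacept monotherapy".

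**The concern.** The inclusion value is the reference for the on-study 20% rule and, as baseline, for the 24-month test. If a patient was already losing function, that reference is one point on a falling line. Without a control arm, whatever decline continues appears as change during reduced immunosuppression.

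Two results could be affected. The first is the eGFR endpoint, which absorbs any continuing decline, slow or steep. The second is the percent converted: a decline steep enough to reach the 20% limit before the last reduction step can stop weaning for a reason unrelated to weaning.

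The protocol's own terms show the gap. A fall from 75 to 42 ml/min in the 6 months before entry (33/75 = 44%) satisfies section 4.1. The same fall on study would fail the section 5.1 stability condition and, if unexplained, meet the biopsy criterion.

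**Working it through.** **Inputs.** From the documents: 20 patients, one arm, 24 months of follow-up; entry floor 40 ml/min; on-study limit 20%; last reduction step at month 10 (timeline table, section 5.1); two-sided 0.05 (section 6). The documents give no SD of eGFR change, no rate of decline, no share of decliners and no basis for the 20, so there is no planned figure to reproduce. Values for these below are assumptions.

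**1. What the floor admits.** Loss before entry = (start - entry)/start. Falls to 41 from 50, 60, 70 and 80 are losses of 18%, 32%, 41% and 49%. A fall from 60 to 45 is 15/60 = 25%. All meet the eGFR criterion.

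**2. Effect on the eGFR test.** Let k of 20 patients decline at s ml/min/year, with no effect of weaning, and let f = k/20.

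- Mean drift over 24 months = f × 2s.
- SD of change = √(SD² + f(1 - f)(2s)²).
- The chance of p < 0.05 comes from the noncentral t distribution with n = 20.

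| k | s | SD | Drift | SD with mixture | Chance of p < 0.05 |
|---|---|---|---|---|---|
| 2 | 4 | 12 | -0.8 | 12.2 | 6% |
| 2 | 4 | 8 | -0.8 | 8.4 | 7% |
| 5 | 8 | 10 | -4.0 | 12.2 | 29% |
| 5 | 12 | 12 | -6.0 | 15.9 | 36% |
| 5 | 12 | 8 | -6.0 | 13.1 | 49% |

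The nominal figure is 5%, counting both directions. In the first row the 6% is made up of 4.6% falls and 1.3% rises; with no drift each would be 2.5%.

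**3. Effect on weaning.** For a linear decline from inclusion value B, the 20% limit is reached by month 10 when the yearly slope is at least 12 × 0.20B/10 = 0.24B. For B = 41, 50 and 60 that is 9.8, 12.0 and 14.4 ml/min/year. The value 6 months before entry would be B + 0.12B = 45.9, 56.0 and 67.2, so all three are eligible.

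Slower decline behaves differently. At 4 ml/min/year from 41, the limit is reached at 12 × 8.2/4 = 24.6 months, and 8 ml/min is lost by month 24.

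The patient who went from 60 to 45 shows both cases. At the same 2.5 ml/min/month, the 9 ml/min limit is reached at 9/2.5 = 3.6 months, before the month 4 step. That rate cannot last 24 months (2.5 × 24 = 60, more than 45). At a quarter of it (0.625/month), the limit is reached at 9/0.625 = 14.4 months, after the last step. The 24-month loss is then 15 ml/min, which moves the mean of 20 by 15/20 = 0.75. The halt route therefore needs a steep decline, while the endpoint route does not.

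**4. Would an entry cut-off solve it?** Take the obvious candidate: inclusion eGFR no more than 20% below the highest value of the previous 6 months. A steady decliner at r per month is excluded only if B/(B + 6r) < 0.8, that is r > B/24. Such a patient would reach the on-study limit before 0.2B/(B/24) = 4.8 months. One who reaches it at month 10 lost 0.12/1.12 = 10.7% before entry and still enrols.

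The cut-off also acts on noise. I simulated truly flat patients with seven monthly values and independent normal errors. At an assumed within-patient CV of 5%, 8% and 10%, it excludes 0.4%, 9% and 19% of them. It leaves the retained inclusion values 0.1%, 1.3% and 2.9% too high. At eGFR 50, 2.9% is about 1.5 ml/min of later apparent loss.

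**5. How precise is a 6-month slope?** With seven monthly values the time deviations have sum of squares 28, so SE = 12σ/√28 per year. At eGFR 50 and the same CVs, σ = 2.5, 4 and 5, giving 5.7, 9.1 and 11.3 ml/min/year for one patient. For the mean of 20, dividing by √20 gives 1.3, 2.0 and 2.5 from measurement noise alone.

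**The case against.** The strongest reply has four parts.

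- **Other criteria filter decliners.** Entry also requires dd-cfDNA below 1%, a quiescent Trugraf signature, no DSA, no BK viremia, no prior biopsy-proven rejection and limited proteinuria. An investigator could also refuse an obvious decliner on the word *stable*. This makes the extreme examples less likely. It does not exclude non-immune decline with little proteinuria, and the written definition does not require refusal.
- **The halt is not automatic.** A reader might infer that a prior decliner will be counted as a weaning failure. The documents do not support that. Section 4.4 halts only for an unexplained, confirmed fall, and a documented earlier decline could be an explanation. Section 5.1 has no such exemption, so the outcome depends on which section is applied. Failed weaning is not an endpoint, and no section defines who counts as converted or the denominator.
- **The size is assumed.** This stands. One slow decliner moves the mean by only 0.75 ml/min in the example above.
- **A single-arm pilot cannot attribute change anyway.** This stands in part: a flat prior course would not prove causation either. But each patient's own earlier course is the only within-patient comparator the design offers, and the plan does not use it.

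**Conclusion.** The point holds in limited form. The entry definition is a level, the on-study definition is a change, and no pre-inclusion course enters the analysis, so a continuing prior decline is carried into the 24-month eGFR comparison. Under the assumed ranges (2 to 5 of 20 declining at 4 to 12 ml/min/year, SD of change 8 to 12 ml/min), the effect runs from negligible to serious; the documents cannot place the trial within that range.

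The effect on weaning is conditional. It needs roughly 10 to 14 ml/min/year or more for inclusion values of 41 to 60, and it needs section 5.1 to be applied without the exemption in section 4.4. Each such halt would be worth 1/20 = 5 percentage points, if the denominator is all 20 enrolled.

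A reader might also infer that the primary endpoint is biased. That is not shown: it is biopsy-proven rejection, and eGFR bears on it only by prompting a biopsy. Nor does the gap justify the single-value entry cut-off checked above, which misses most slower decliners and removes some stable patients by chance.

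**What to change.** 1. **Section 6, eGFR.** Estimate each participant's pre-inclusion slope from the routine values of the 6 months already reviewed for eligibility. Compare the on-study slope with it within patient, for example by a mixed model with a change of slope at inclusion, and report this beside the planned baseline-to-24-month comparison.
2. **Section 6, percent converted.** State the numerator and denominator. Identify which halts occurred in patients with a pre-existing decline.
3. **Sections 4.1, 5.1 and 4.4.** Reconcile the entry and on-study definitions of stability, and the two 20% rules, which differ on explained falls and on confirmation. Which rule should apply is for the investigators to decide.
4. **If a limit on change is added at entry,** base it on averaged values or on the slope, not on one inclusion value against the 6-month maximum.

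The cost is a small amount of extra analysis and extraction of values already in the records. The limitation is precision: a 6-month slope is too imprecise to classify one patient reliably, so the comparison should be read mainly at group level and the individual slopes treated as descriptive.
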